## **10.2. Data Monitoring**

The PI and collaborators will ensure all aspects of data quality, including monitoring for adherence to consent procedures, inclusion and exclusion criteria, valid abstraction, correct entry, timeliness and responsiveness to data queries.

Data will be collected and stored with the participant ID code only. The master enrollment log linking subject identifiers with study ID numbers will be kept in a password-protected database on the OB/GYN department's internal server separate from the data. Data collection forms will be used. Data on these forms devoid of personal identifiers will be securely stored at our perinatal research division. The research coordinator will be available to monitor the data and correct any discrepancies based on source documents if needed.

Data quality and safety of subjects will be monitored also by sponsor's representative to assure independent review. Any issue identified will be followed up closely to assure the subjects' safety and adherence to protocol as well as data quality.

The sponsor's monitor performs monitoring remotely; therefore, they only need to formally conduct in person monitoring visits to review the informed consents and other paper documents. One monitoring visit for approximately every 60 randomized subjects is sufficient. The monitoring visit frequency depends on enrollment, if enrollment increases, the frequency will increase as well. In conclusion, we expect approximately 2-4 monitoring visits per year.

## **11. Procedures to Maintain Confidentiality**

Each subject will be assigned a study number (Subject ID) with personally identifiable information deleted or removed. This Subject ID will be unique for every subject and will not contain any study group identifier. Subjects' information will be de-identified and tagged with a number. Data will be collected and stored on a UTMB or CUMC password-protected computer in a locked room.

## **12. Potential Benefit**

This study has the potential benefit to show that outpatient pre-induction cervical ripening with Dilapan-S® decreases length of hospital stay without affecting maternal and neonatal outcomes. Ultimately, this may reduce the health care costs and workload associated with induction of labor and improve maternal neonatal early bonding.

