### **13.3. Analysis of secondary outcomes**

Nominal variables will be evaluated in the same manner as the primary outcome. Continuous variables will be summarized (minimum, maximum, mean, standard deviation, median, lower and upper quartile) and the difference between groups will be tested by t-test or Wilcoxon-Mann-Whitney test as appropriate. For time-to-event outcomes, Kaplan-Meier will be used to estimate the survival curves and log-rank test will be used to test the difference between groups by ITT analysis.

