### **13.4. Sample size**

Sample size was calculated based on the determination of superiority. The primary outcome is proportion of women with hospital stay >48 hours. For the sample size calculation, we assumed the proportion in the control arm would be 54% ( $p_i = 0.54$ ). This is based on current experience at UTMB and unpublished data from an international registry trial (9). We estimate that outpatient intervention would decrease this proportion by 30% ( $p_{ii} = 0.378$ ). Based on 85% power and two-sided alpha of 0.05, the total sample size per group required would be 169. Accounting for 10% of premature terminations or drop outs the sample size per group becomes 188, making the total sample size needed 376.

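### Section 12 hopes to show no effect on maternal and neonatal outcomes, but the only stated comparison of binary harms is a difference test that would usually miss a doubling of the rarer ones

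*Combined protocol and SAP*

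**What the plan says.** Section 12 (Potential Benefit) says the study may show that outpatient ripening "decreases length of hospital stay without affecting maternal and neonatal outcomes".

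Section 6.2 lists the harms among the secondary outcomes: an adverse neonatal outcome, composite and by component (Apgar below 7 at 1, 5 and 10 minutes, cord arterial pH below 7.1, NICU admission), and maternal and neonatal complications up to two weeks after delivery. Section 13.3 gives their analysis: "Nominal variables will be evaluated in the same manner as the primary outcome". Section 13.2 defines that manner as a chi-square test of the difference between two proportions.

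Section 13.1 defines a Safety population for comparing the two settings but attaches no estimate, interval, margin or decision rule. Section 13.4 is explicit about the target of the sizing: "Sample size was calculated based on the determination of superiority", on stay over 48 hours. The opening of section 13 says it gives basic principles only and that a statistical analysis plan will be approved before database lock. The supplied text contains no such plan.

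**The concern.** A statement that one setting shortens stay without affecting harm has two halves. The first is a superiority claim, for which the trial is properly sized. The second is a claim of no important difference, which a test of difference cannot establish. A non-significant chi-square is informative about harm only if the test would have had a good chance of detecting the harm that matters. Otherwise the upper confidence limit has to show what excess is excluded, and the protocol text plans no interval.

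At stake is how the harm results will be summarised. If infection or NICU admission truly doubled, the stated test would more often than not return a non-significant result, and nothing in the text stops that from being summarised in the words of section 12. The cost analysis in section 3 adds to the risk: it uses cost minimization, whose premise is that the compared strategies have been assumed or shown to be equally effective.

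**Working it through.** **Inputs.** Design figures are from section 13.4: "Based on 85% power and two-sided alpha of 0.05"; control proportion 0.54; 30% relative reduction, so 0.54 × 0.70 = 0.378; "the total sample size per group required would be 169"; 188 per group after 10% loss. Harm rates are from the table of 444 inpatient Dilapan-S subjects in section 3: maternal infection 14 (3.2%), NICU admission 6 (1.4%). Section 3 describes the 376 as consented subjects, and some will not reach randomization, so 188 analysable per arm is the most favourable case.

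**Step 1: reproduce the plan's sample size.** With p̄ = (p1 + p2)/2,

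n = [1.96·√(2p̄(1−p̄)) + 1.036·√(p1(1−p1) + p2(1−p2))]² / (p1 − p2)²

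Here p̄ = 0.459, so n = (1.96 × 0.7047 + 1.036 × 0.6954)² / 0.162² = 168.3, rounded up to 169. Then 169/0.9 = 187.8, rounded up to 188, and 2 × 188 = 376. The stated size is correct for the primary outcome.

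**Step 2: power of the same test against a doubling of harm.** The normal approximation is

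power = Φ{ [|p2 − p1|·√n − 1.96·√(2p̄(1−p̄))] / √(p1(1−p1) + p2(1−p2)) }

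- Infection, 3.2% to 6.4%, n = 188: (0.4388 − 0.5925)/0.3015 = −0.51, power 0.305.
- NICU admission, 1.4% to 2.8%, n = 188: (0.1920 − 0.3974)/0.2025 = −1.01, power 0.155.

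The approximation is rough at low rates. The figures below therefore come from exact binomial enumeration of the uncorrected chi-square.

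| Control rate, doubled | Source of rate | Power, 188 per arm | Power, 169 per arm |
|---|---|---|---|
| 1.4% | NICU admission, section 3 | 14% | 13% |
| 3.2% | maternal infection, section 3 | 30% | 28% |
| 5% | assumed | 46% | 42% |
| 6% | assumed | 54% | 50% |
| 8% | assumed | 68% | 63% |
| 10% | assumed | 78% | 74% |

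A true doubling would be missed about 70% of the time for infection and 86% for NICU admission at 188 per arm. Against a tripling, power is 74% and 37%. By the Step 1 formula at 80% power (0.842 replacing 1.036), detecting a doubling needs 700 per arm at 3.2% and 1,646 at 1.4%.

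By the approximation, power against a doubling passes 50% at a control rate of about 5.7% (6.2% with 169 per arm) and 80% at about 10.5% (11.5%).

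**Step 3: what an interval would show.** Suppose the arms come out identical. The Newcombe 95% half-width is √[(p − l)² + (u − p)²], where l and u are the Wilson limits for one arm.

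- 6/188 in each arm (3.2%): Wilson limits 1.5% and 6.8%, half-width 4.0 points. The excess not excluded takes 3.2% to 7.2%, about 2.2 times.
- 3/188 in each arm (1.6%): Wilson limits 0.5% and 4.6%, half-width 3.2 points. The excess not excluded takes 1.6% to 4.8%, about 3 times.
- 15/188 (8.0%) and 19/188 (10.1%): half-widths 5.7 and 6.2 points. At these rates identical arms would exclude a doubling.

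The same counts in 169 per arm give intervals about 10% wider.

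**The case against.** **Nothing says a non-significant test will be read as safety.** This stands. Section 12 describes a potential benefit, not a hypothesis or decision rule, and the secondary objective in section 3 is only to compare these outcomes. A reader might infer that the sponsor intends to treat p > 0.05 as proof of safety and to support home ripening on that basis. The documents do not say so. What they do support is narrower: the text gives no other route to a no-effect statement and no safeguard against that reading.

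**Detail is deferred to a later plan.** This also stands, so one can say only that no interval or limit appears in the protocol text, not that none will ever be planned. The deferral supplies no rule for harms; it shows where one can be added.

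**The result depends on the rate.** It does. A reader might infer that the test would usually miss a doubling of any harm. The registry rows run from 0.2% to 25%, and the documents give no rate for the neonatal composite, which includes Apgar below 7 at 1 minute, or for the two-week complications. Above about 6% a doubling would be detected more often than not. The low-power statement is confined to the rarer individual events.

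**The registry is an imperfect benchmark.** Three of its six NICU admissions were for growth restriction or a congenital cardiac abnormality, which section 7.2 excludes here. A lower NICU rate would reduce power further, so this does not rescue the plan.

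**There are other safety provisions.** There is a Safety population, device-related event reporting (section 10.1) and an individual participant data meta-analysis with other centers (section 3). Pooling is a sensible way to study rare events. None of these provides a between-arm estimate with a limit on excess harm from this trial.

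**Conclusion.** The concern holds for the rarer individual harms. At the section 3 rates, the stated chi-square has 30% power (28% after planned losses) to detect a doubling of maternal infection and 14% (13%) for NICU admission. Even identical observed results would leave roughly a 2.2-fold and a 3-fold risk unexcluded. These figures assume that the registry rates apply to the inpatient arm, that the test is uncorrected and two-sided at 0.05, and that 188 or 169 per arm are analysable.

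For the neonatal composite and the two-week complications the documents give no rate, so the conclusion is conditional: 46% power if the control rate is 5%, rising to 78% at 10%, with 188 per arm.

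The primary outcome's sample size is correct and is not at issue. Low power for rare secondary harms is common in trials sized on another endpoint. The defect is pairing it with a no-effect aspiration while the text gives only a bare difference test.

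**What to change.** In section 13.3, or in the statistical analysis plan before database lock:

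- Report maternal infection, NICU admission, the neonatal composite and the two-week maternal and neonatal complications as risk differences, outpatient minus inpatient, with 95% Newcombe or Miettinen-Nurminen confidence intervals.
- Give the upper limit as the largest excess risk not excluded.
- State that a non-significant test will not be reported as absence of effect.

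In section 12, replace *without affecting* with *and to estimate the effect on*. Do not attach one fixed precision figure, because precision changes with the event rate. If precision is quoted, give it by rate, for identical arms: about 3.2 points at 3/188, 4.0 at 6/188, 5.7 at 15/188 and 6.2 at 19/188, and about 10% more at 169 per arm.

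The cost is wording only: no added participants or data, and no change to the primary analysis. The downside is a more modest safety claim.

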## **13. Biostatistics/Sample Size**

Basic principles for an evaluation of the study are presented in this section, more detailed description of how to analyze collected data will be specified in statistical analysis plan (SAP) which will be written and approved before the database lock. The statistical analysis including the data from the additional site will be specified in the SAP.

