### **5.3. Randomization**

After Dilapan-S® placement, and if the subject remains eligible, subject will be randomized to the outpatient group or the inpatient group. A confidential computer-generated simple randomization scheme will be prepared and provided by independent vendor (PharmTest, s.r.o., Czech Republic) to our study coordinator. The currently used randomization code will be replaced by 2 randomization codes, 1 of them for CUMC site (both clinics will use the same randomization sequence. The randomization envelopes to be used at CUMC will be provided by UTMB).

A randomization log with group assignment, subject name, and medical record *number* will be used to track the randomization process. The subject will be included in the analysis by intent-to-treat once the randomization assignment has been made.

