### **VISIT #2**

#### **5.5. Labor Induction and Labor**

Management of the subject after the initial 12 hours of pre-induction or following the earlier removal or spontaneous expulsion of the dilator will be the same for both groups and at the discretion of the clinical team. Additional ripening (mechanical or prostaglandins) and/or oxytocin may or may not be needed. If needed, duration, type and dose of additional ripening agents and oxytocin will be documented.

Routine intrapartum care will be provided and relevant data collected by the subject's managing obstetrical team.

Trained and experienced research staff will be responsible for all research data abstraction. The PI and collaborators will review and validate the outcomes. If there is uncertainty, a second investigator will review the chart, discuss with the other investigators as needed, and make a final determination regarding the outcome.

Subjective assessment data will be collected, using adequate validated tools either after Dilapan-S® extraction or any time prior labor or post-partum (Appendix 3) at the time point best suitable for both the subject and the study team.

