## **6. Study Outcomes**

### **6.1. Primary Outcomes**

Rate of hospital stay longer than 48 hours (from admission to discharge)

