#### *Intent-to-treat Population (ITT)*

ITT includes all patients that were randomized into the study and primary outcome has been obtained. ITT subjects will be analyzed in accordance with their randomized study treatment (i.e. in the treatment group they were originally allocated, regardless of treatment actually received). ITT will be used for evaluation of the baseline characteristics and as the primary population for efficacy assessments. Other predefined subgroup interaction analysis for cervical dilation at randomization, parity ( $P=0$  vs  $P>0$ ), or  $BMI > 30 \text{ kg/m}^2$  will be also performed.

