### **13.2. Analysis of primary outcome**

Primary outcome of the study is the rate of hospital stay longer than 48 hours. Proportion of patients in the outpatient and inpatient group will be calculated and their difference will be tested by chi-square test by ITT analysis.

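### The SAP need only be approved before database lock, so whether the primary test is pooled or stratified by site can be settled after results by arm are visible

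*Combined protocol and SAP*

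**What the plan says.** Section 13 presents its contents as basic principles and refers the detail to a "statistical analysis plan (SAP) which will be written and approved before the database lock". It gives no earlier deadline. It then adds: "The statistical analysis including the data from the additional site will be specified in the SAP".

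The core of the primary analysis is nevertheless in the protocol. Section 6.1 defines the endpoint as a hospital stay over 48 hours, counted from admission to discharge. Section 13.2 says of the two proportions that "their difference will be tested by chi-square test by ITT analysis". Section 13.1 makes ITT the primary efficacy population, analysed by randomised arm, and Section 13.4 sets a two-sided alpha of 0.05. Section 13.2 does not mention site.

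On who knows what, Section 5.3 describes "A randomization log with group assignment, subject name" and record number together. Section 5.5 says "The PI and collaborators will review and validate the outcomes". Neither section describes masking of those who validate or analyse outcomes. Sections 3 and 5.3 provide separate randomisation sequences for UTMB and CUMC, and Section 5.3 shows that these replace a code already in use.

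**The concern.** Approving an SAP before database lock protects the type I error only if those who settle it cannot see outcomes by arm until then. Here the arms are inpatient and outpatient ripening, so assignment is visible by design. The documents place no restriction on by-arm summaries before the SAP is approved.

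The site question bears on the primary result. A pooled chi-square test and a site-stratified test can fall on opposite sides of 0.05 in the same data. The sites may also differ in ways that affect stay: under Section 5.4.1, outpatients at CUMC have only the home option, while the hotel is otherwise offered. If the rule is settled late, a reader of the final report could not tell whether it was chosen blind to the result.

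**Working it through.** **1. The plan's own figure.** Inputs from Section 13.4: control rate 0.54, a 30% relative reduction (0.54 × 0.7 = 0.378), power 85%, two-sided alpha 0.05. With mean rate 0.459 and difference 0.162:

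n = [1.960 × √(2 × 0.459 × 0.541) + 1.036 × √(0.54 × 0.46 + 0.378 × 0.622)]² / 0.162² = (1.381 + 0.721)² / 0.02624 ≈ 168.4, so 169 per group.

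169 / 0.90 = 187.8, so 188 per group and 376 in total. Both figures reproduce. The calculation rests on the unstratified comparison.

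**2. What is fixed and what is open.**

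| Element | Status |
|---|---|
| Endpoint | Fixed, Section 6.1 |
| Test family and population | Fixed, Sections 13.1 and 13.2 |
| Alpha | Fixed, Section 13.4 |
| Pooled or stratified by site | Left to the SAP, Section 13 |

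**3. Size of the open choice.** I simulated trials with no treatment effect: 2 × 169 = 338 women, simple randomisation within site, overall event rate 54%, 200,000 trials per setting. The documents give neither the CUMC share nor the difference in event rate between sites, so both are assumptions shown as a range.

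- Pooled: the ordinary chi-square test.
- Stratified: Cochran-Mantel-Haenszel, [Σ(x₁ − n₁m/n)]² / Σ[n₁n₀m(n − m) / (n²(n − 1))], summed over sites. Within a site, x₁ is the number of events in one arm, n₁ and n₀ are the arm sizes, m is the total events and n the total women.
- Both are compared with 3.84. A late choice counts as a false positive if either test rejects.

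Either test fixed in advance rejects in 4.9-5.1% of trials. Rejection rate (%) when the better of the two may be chosen:

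| CUMC share | Gap 0 | Gap 10 points | Gap 20 points | Gap 30 points |
|---|---|---|---|---|
| 10% | 5.2 | 5.3 | 5.6 | 5.8 |
| 20% | 5.2 | 5.3 | 5.7 | 6.1 |
| 30% | 5.2 | 5.4 | 5.9 | 6.3 |
| 50% | 5.2 | 5.5 | 5.9 | 6.4 |

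Reversing which site has the higher rate moves a cell by at most about 0.2 points. Holding UTMB at 54% and moving only CUMC gives 5.2-6.5%.

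**4. Cost of stratifying.** With the plan's 30% relative reduction at each site and the overall control rate at 54%, the pooled test has about 85% power. The stratified test has about 0.2 points less with no site gap, the same to within 0.1 point at a gap of 10, 0.2-1.0 points more at a gap of 20, and 0.6-2.2 points more at a gap of 30.

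**The case against.** The strongest reply is that the primary analysis is already specified and that a plain chi-square test, read literally, is a pooled one. An SAP that replaced it would visibly depart from Section 13.2. Most of this stands: a reader might infer from the lock deadline that the whole primary analysis is still open, and the documents do not support that. The reply does not reach site handling, because Section 13 expressly hands the analysis with the second site to the SAP.

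A reader might also infer that CUMC could be left out altogether, which would give a larger inflation (7.2-9.5% in a three-way choice). The text points against it. Section 3 counts subjects at both sites. Section 5.3 includes each woman in the ITT analysis once she is assigned. Section 13.1 says "ITT includes all patients that were randomized into the study and primary outcome has been obtained", with no exception for site. Section 13 itself speaks of including the additional site's data.

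The unspecified choice in Section 13.3, "tested by t-test or Wilcoxon-Mann-Whitney test as appropriate", might look like further freedom over the primary result. It governs continuous secondary outcomes, including hours of stay, and has no bearing on the primary alpha.

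Finally, knowing individual assignments is not the same as seeing results by arm. Sections 10.2 and 11 keep data under an ID code that carries no group identifier. That is fair, but it does not amount to masking of analysts, and the documents do not say who writes the SAP.

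**Conclusion.** The point holds in a narrow form. Section 13 lets the SAP be approved as late as database lock and defers the role of site to it, in a trial where arm is known to staff and no analyst masking is stated. For the primary result, this leaves the choice between pooling and stratifying by site. The inflation is modest: from 5% to at most about 5.2-6.4%, with 6% or more only at an assumed site gap of 20-30 points. These figures assume that the smaller p-value is chosen deliberately, so they are upper bounds.

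Nothing in the documents shows that anyone examined outcomes by arm, and that should not be inferred. What is missing is a safeguard. No separate SAP text is available, so its approval date and its site rule cannot be checked.

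**What to change.** In Section 13.2, state that all randomised women from both sites enter the primary analysis, under the ITT rule of Section 13.1, and that the comparison is stratified by site with the Cochran-Mantel-Haenszel test. This matches the separate randomisation sequences in Sections 3 and 5.3. A pooled test fixed in advance would also hold 5%. Stratifying is preferred because it follows the randomisation, costs essentially no power and gains up to about 2 points if the sites differ.

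In Section 13, replace the lock deadline with a requirement that the SAP be approved and dated before any efficacy outcome is summarised by arm. Safety review should be exempt. Any analysis decision made later should be labelled post hoc.

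The cost is wording, an earlier SAP, and dated amendments for later changes. The sample size stays at 169 evaluable and 188 randomised per group, 376 in total.

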### **13.1. Study populations**

#### *All Randomized population*

This will be comprised for all subjects who had Dilapan-S® inserted and were randomized. This includes patients who terminated participation for any reason (lost to follow-up or did not return to hospital for admission). We will perform a sensitivity analysis (worst case scenario), where we will consider these subjects to have reached the primary outcome.

